#### **5.4.1 Acceptable Concomitant Medications**

All treatments that the investigator considers necessary for a subject's welfare may be administered at the discretion of the investigator in keeping with the community standards of medical care. All concomitant medication will be recorded on the case report form (CRF) including all prescription, over-the-counter (OTC), herbal supplements, and IV medications and fluids. If changes occur during the trial period, documentation of drug dosage, frequency, route, and date may also be included on the CRF.

All concomitant medications received within 28 days before the first dose of trial treatment and 30 days after the last dose of trial treatment should be recorded. Concomitant medications administered after 30 days after the last dose of trial treatment should be recorded for SAEs and ECIs as defined in Section 7.2.

#### **5.4.2 Prohibited Concomitant Medications**

Subjects are prohibited from receiving the following therapies during the Screening and Treatment Phase of this trial:

- Biological therapy
- Immunotherapy not specified in this protocol
- Chemotherapy not specified in this protocol
- Investigational agents other than Pembrolizumab
- Live vaccines within 30 days prior to the first dose of trial treatment and while participating in the trial. Examples of live vaccines include, but are not limited to, the following: measles, mumps, rubella, varicella/zoster, yellow fever, rabies, BCG, and typhoid vaccine.
- Systemic glucocorticoids should be avoided if possible. Steroids are allowed as anti-emetic around Cisplatin dosing, as short bursts of 5-7 days if required for clinical indication (ie COPD) or to modulate symptoms from an event of clinical interest of suspected immunologic etiology. The chronic use of physiologic doses of corticosteroids may be approved after consultation with the Sponsor.

Subjects who, in the assessment by the investigator, require the use of any of the aforementioned treatments for clinical management other than specified as allowed, should be removed from the trial. Subjects may receive other medications that the investigator deems to be medically necessary.

The Exclusion Criteria describes other medications which are prohibited in this trial. There are no prohibited therapies during the Post-Treatment Follow-up Phase.

## 5.5 Rescue Medications & Supportive Care

### 5.5.1 Supportive Care Guidelines

Subjects should receive appropriate supportive care measures as deemed necessary by the treating investigator.

#### 5.5.1.1 Pembrolizumab

Suggested supportive care measures for the management of adverse events with potential immunologic etiology are outlined below and in greater detail in the investigator's brochure. Where appropriate, these guidelines include the use of oral or intravenous treatment with corticosteroids as well as additional anti-inflammatory agents if symptoms do not improve with administration of corticosteroids. Note that several courses of steroid tapering may be necessary as symptoms may worsen when the steroid dose is decreased. For each disorder, attempts should be made to rule out other causes such as metastatic disease or bacterial or viral infection, which might require additional supportive care. The treatment guidelines are intended to be applied when the investigator determines the events to be related to Pembrolizumab.

Note: if after the evaluation the event is determined not to be related, the investigator is instructed to follow the ECI reporting guidance but does not need to follow the treatment guidance. Refer to Section 5.2.1 for dose modification.

It may be necessary to perform conditional procedures such as bronchoscopy, endoscopy, or skin photography as part of evaluation of the event.

- **Pneumonitis:**

- For **Grade 2 events**, treat with systemic corticosteroids. When symptoms improve to Grade 1 or less, steroid taper should be started and continued over no less than 4 weeks.
- For **Grade 3-4 events**, immediately treat with intravenous steroids. Administer additional anti-inflammatory measures, as needed.
- Add prophylactic antibiotics for opportunistic infections in the case of prolonged steroid administration.

- **Diarrhea/Colitis:**

Subjects should be carefully monitored for signs and symptoms of enterocolitis (such as diarrhea, abdominal pain, blood or mucus in stool, with or without fever) and of bowel perforation (such as peritoneal signs and ileus).

- All subjects who experience diarrhea/colitis should be advised to drink liberal quantities of clear fluids. If sufficient oral fluid intake is not feasible, fluid and electrolytes should be substituted via IV infusion. For Grade 2 or higher diarrhea, consider GI consultation and endoscopy to confirm or rule out colitis.

- For **Grade 2 diarrhea/colitis** that persists greater than 3 days, administer oral corticosteroids.
- For **Grade 3 or 4 diarrhea/colitis** that persists > 1 week, treat with intravenous steroids followed by high dose oral steroids.
- When symptoms improve to Grade 1 or less, steroid taper should be started and continued over no less than 4 weeks.
- **Type 1 diabetes mellitus (if new onset, including diabetic ketoacidosis [DKA]) or ≥ Grade 3 Hyperglycemia, if associated with ketosis (ketonuria) or metabolic acidosis (DKA)**
  - For **T1DM or Grade 3-4 Hyperglycemia**
    - Insulin replacement therapy is recommended for Type I diabetes mellitus and for Grade 3-4 hyperglycemia associated with metabolic acidosis or ketonuria.
    - Evaluate patients with serum glucose and a metabolic panel, urine ketones, glycosylated hemoglobin, and C-peptide.
- **Hypophysitis:**
  - For **Grade 2** events, treat with corticosteroids. When symptoms improve to Grade 1 or less, steroid taper should be started and continued over no less than 4 weeks. Replacement of appropriate hormones may be required as the steroid dose is tapered.
  - For **Grade 3-4** events, treat with an initial dose of IV corticosteroids followed by oral corticosteroids. When symptoms improve to Grade 1 or less, steroid taper should be started and continued over no less than 4 weeks. Replacement of appropriate hormones may be required as the steroid dose is tapered.
- **Hyperthyroidism or Hypothyroidism:**

Thyroid disorders can occur at any time during treatment. Monitor patients for changes in thyroid function (at the start of treatment, periodically during treatment, and as indicated based on clinical evaluation) and for clinical signs and symptoms of thyroid disorders.

  - **Grade 2** hyperthyroidism events (and **Grade 2-4** hypothyroidism):
    - In hyperthyroidism, non-selective beta-blockers (e.g. propranolol) are suggested as initial therapy.
    - In hypothyroidism, thyroid hormone replacement therapy, with levothyroxine or liothyroinine, is indicated per standard of care.
  - **Grade 3-4** hyperthyroidism
    - Treat with an initial dose of IV corticosteroid followed by oral corticosteroids. When symptoms improve to Grade 1 or less, steroid taper should be started and continued over no less than 4 weeks. Replacement of appropriate hormones may be required as the steroid dose is tapered.
- **Hepatic:**

- For **Grade 2** events, monitor liver function tests more frequently until returned to baseline values (consider weekly).
  - Treat with IV or oral corticosteroids
- For **Grade 3-4** events, treat with intravenous corticosteroids for 24 to 48 hours.
- When symptoms improve to Grade 1 or less, a steroid taper should be started and continued over no less than 4 weeks.

- **Renal Failure or Nephritis:**
  - For **Grade 2** events, treat with corticosteroids.
  - For **Grade 3-4** events, treat with systemic corticosteroids.
  - When symptoms improve to Grade 1 or less, steroid taper should be started and continued over no less than 4 weeks.
- **Management of Infusion Reactions:** Signs and symptoms usually develop during or shortly after drug infusion and generally resolve completely within 24 hours of completion of infusion.

Table 4 below shows treatment guidelines for subjects who experience an infusion reaction associated with administration of Pembrolizumab (MK-3475).

Table 4 Infusion Reaction Treatment Guidelines

NCI CTCAE Grade	Treatment	Premedication at subsequent dosing
Grade 1 Mild reaction; infusion interruption not indicated; intervention not indicated	Increase monitoring of vital signs as medically indicated until the subject is deemed medically stable in the opinion of the investigator.	None
Grade 2 Requires infusion interruption but responds promptly to symptomatic treatment (e.g., antihistamines, NSAIDS, narcotics, IV fluids); prophylactic medications indicated for <=24 hrs	
Stop Infusion and monitor symptoms.
 
Additional appropriate medical therapy may include but is not limited to:
 
 
IV fluids
 
Antihistamines
 
NSAIDS
 
Acetaminophen
 
Narcotics
 
 
Increase monitoring of vital signs as medically indicated until the subject is deemed medically
	
Subject may be premedicated 1.5h (<math>\pm</math> 30 minutes) prior to infusion of Pembrolizumab (MK-3475) with:
 
 
Diphenhydramine 50 mg po (or equivalent dose of antihistamine).
 
Acetaminophen 500- 1000 mg po (or equivalent dose of antipyretic).
 

	
stable in the opinion of the investigator.
 
If symptoms resolve within one hour of stopping drug infusion, the infusion may be restarted at 50% of the original infusion rate (e.g., from 100 mL/hr to 50 mL/hr). Otherwise dosing will be held until symptoms resolve and the subject should be premedicated for the next scheduled dose.
 
Subjects who develop Grade 2 toxicity despite adequate premedication should be permanently discontinued from further trial treatment administration.
	

Grades 3 or 4
 
Grade 3: Prolonged (i.e., not rapidly responsive to symptomatic medication and/or brief interruption of infusion); recurrence of symptoms following initial improvement; hospitalization indicated for other clinical sequelae (e.g., renal impairment, pulmonary infiltrates)
 
Grade 4: Life-threatening; pressor or ventilatory support indicated
	
Stop Infusion.
 
Additional appropriate medical therapy may include but is not limited to:
 
 
IV fluids
 
Antihistamines
 
NSAIDS
 
Acetaminophen
 
Narcotics
 
Oxygen
 
Pressors
 
Corticosteroids
 
Epinephrine
 
 
Increase monitoring of vital signs as medically indicated until the subject is deemed medically stable in the opinion of the investigator. Hospitalization may be indicated.
 
Subject is permanently discontinued from further trial treatment administration.
	
No subsequent dosing

Appropriate resuscitation equipment should be available in the room and a physician readily available during the period of drug administration.

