#### **5.2.2.4 Dose Modification**

##### **5.2.2.4.1 Pembrolizumab - Dose Modification and toxicity management for immune-related AEs associated with pembrolizumab and combination therapy**

Adverse events (both non-serious and serious) associated with Pembrolizumab exposure may represent an immunologic etiology. These adverse events may occur shortly after the first dose or several months after the last dose of treatment. Pembrolizumab must be withheld for drug-related toxicities and severe or life-threatening AEs as per Table 3 below. See Section 5.6.1 and the most current investigator's brochure for supportive care guidelines, including use of corticosteroids.

Table 3

Dose Modification Guidelines for Drug-Related Adverse Events

General instructions:				
Immune-related AEs	Toxicity grade or conditions (CTCAE v 4.0)	Action taken to Pembrolizumab	Immune Related AE management with corticosteroid and/or other therapies	Monitor and follow-up
Pneumonitis	Grade 2	Withhold	
 
Administer corticosteroids (initial dose of 1-2 mg/kg prednisone or equivalent) followed by taper
 
Add prophylactic antibiotics for opportunistic infections
 
	
 
Monitor participants for signs and symptoms of pneumonitis
 
Evaluate participants with suspected pneumonitis with radiographic imaging and initiate corticosteroid treatment
 

	Grade 3 or 4, or recurrent Grade 2	Permanently discontinue		•
Diarrhea / Colitis	Grade 2 or 3	Withhold	
 
• Administer corticosteroids (initial dose of 1-2 mg/kg prednisone or equivalent) followed by taper
 
	
 
• Monitor participants for signs and symptoms of enterocolitis (ie, diarrhea, abdominal pain, blood or mucus in stool with or without fever) and of bowel perforation (ie, peritoneal signs and ileus). Participants with <math>\geq</math> Grade 2 diarrhea suspecting colitis should consider GI consultation and performing endoscopy to rule out colitis.
 
• Participants with diarrhea/colitis should be advised
 

	Grade 4	Permanently discontinue		to drink liberal quantities of clear fluids. If sufficient oral fluid intake is not feasible, fluid and electrolytes should be substituted via IV infusion.
--	---------	-------------------------	--	---

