#### **7.2.4 Evaluating Adverse Events**

An investigator who is a qualified physician will evaluate all adverse events according to the NCI Common Terminology for Adverse Events (CTCAE), version 4.0. Any adverse event which changes CTCAE grade over the course of a given episode will have each change of grade recorded on the adverse event case report forms/worksheets.

All adverse events regardless of CTCAE grade must also be evaluated for seriousness.

Table 6 Evaluating Adverse Events

An investigator who is a qualified physician, will evaluate all adverse events as to:

V4.0 CTCAE Grading	Grade 1	Mild; asymptomatic or mild symptoms; clinical or diagnostic observations only; intervention not indicated.
	Grade 2	Moderate; minimal, local or noninvasive intervention indicated; limiting age-appropriate instrumental ADL.
	Grade 3	Severe or medically significant but not immediately life-threatening; hospitalization or prolongation or hospitalization indicated; disabling; limiting self-care ADL.
	Grade 4	Life threatening consequences; urgent intervention indicated.
	Grade 5	Death related to AE
Seriousness	A serious adverse event is any adverse event occurring at any dose or during any use of Merck product that:	
	† Results in death ; or	
	† Is life threatening ; or places the subject, in the view of the investigator, at immediate risk of death from the event as it occurred (Note: This does not include an adverse event that, had it occurred in a more severe form, might have caused death.); or	
	† Results in a persistent or significant disability/incapacity (substantial disruption of one's ability to conduct normal life functions); or	
	† Results in or prolongs an existing inpatient hospitalization (hospitalization is defined as an inpatient admission, regardless of length of stay, even if the hospitalization is a precautionary measure for continued observation. (Note: Hospitalization [including hospitalization for an elective procedure] for a preexisting condition which has not worsened does not constitute a serious adverse event.); or	
	† Is a congenital anomaly/birth defect (in offspring of subject taking the product regardless of time to diagnosis); or	
	Is a new cancer ; (that is not a condition of the study) or	

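### Section 5.5.1.1 states a longer wait before steroids for Grade 3 or 4 Pembrolizumab-related diarrhea/colitis (more than 1 week) than for Grade 2 (more than 3 days), which is out of line with Table 3

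*Combined protocol and SAP*

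**What the plan says.** Two places in the protocol tell sites how to use steroids for immune-related diarrhea/colitis.

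The first is Table 3 in Section 5.2.2.4.1. For Grade 2 or 3 it withholds Pembrolizumab and says: "Administer corticosteroids (initial dose of 1-2 mg/kg prednisone or equivalent) followed by taper". It attaches no duration condition, although it does not say that steroids must start at once. For Grade 4 it permanently discontinues Pembrolizumab. The lead-in to the table adds: "See Section 5.6.1 and the most current investigator's brochure for supportive care guidelines, including use of corticosteroids".

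The second is the supportive care text in Section 5.5.1.1. For Grade 2 the instruction covers an event "that persists greater than 3 days, administer oral corticosteroids". For Grade 3 or 4 it covers one "that persists > 1 week, treat with intravenous steroids followed by high dose oral steroids". The section describes its measures as suggested, but also says: "The treatment guidelines are intended to be applied when the investigator determines the events to be related to Pembrolizumab".

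Section 5.5.1 leaves supportive care to the treating investigator, and Section 5.4.1 gives similar latitude for concomitant treatment.

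**The concern.** One would expect the trigger for steroids to stay the same or shorten as severity rises. In 5.5.1.1 it lengthens. A site following that section has protocol text that supports waiting more than a week before giving steroids for Grade 3 or 4 immune-related colitis, while a milder case qualifies after more than 3 days. A site following Table 3 sees no such wait for Grade 2 or 3.

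The trial is run at several sites (Section 8.1.4), so the same serious toxicity could be managed on different timetables, with each site able to point to protocol text. What is at stake is the safety of patients who have these events. No efficacy or safety analysis is affected.

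**Working it through.** No statistical formula applies. The check sets the texts side by side, counts the steroid instructions and compares the thresholds.

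**1. Stated wait before steroids, by grade**

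| Grade of diarrhea/colitis | Section 5.5.1.1 | Table 3 (Section 5.2.2.4.1) |
|---|---|---|
| 2 | more than 3 days | none stated |
| 3 | more than 7 days | none stated |
| 4 | more than 7 days | steroid cell blank in the copy reviewed; not used |

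Difference within 5.5.1.1: 7 - 3 = 4 days longer for the graver grades. Taken at face value, the two sections differ up to day 3 for Grade 2 and up to day 7 for Grade 3.

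**2. Is a waiting condition usual in 5.5.1.1?** The steroid instructions tied to a grade are:

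- pneumonitis: 2 (Grade 2; Grade 3-4)
- diarrhea/colitis: 2 (Grade 2; Grade 3 or 4)
- hypophysitis: 2 (Grade 2; Grade 3-4)
- hyperthyroidism: 1 (Grade 3-4)
- hepatic: 2 (Grade 2; Grade 3-4)
- renal: 2 (Grade 2; Grade 3-4)

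Total: 2 + 2 + 2 + 1 + 2 + 2 = 11. Two have a persistence condition, both for colitis; 11 - 2 = 9 have none. Type 1 diabetes has no steroid instruction, and the infusion-reaction options in Table 4 are not counted. For Grade 3-4 pneumonitis the instruction is to "immediately treat with intravenous steroids".

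**3. Does the wait fit the protocol's own grading?** Table 6 in Section 7.2.4 describes Grade 3 as an event with "hospitalization or prolongation or hospitalization indicated" and Grade 4 as "Life threatening consequences; urgent intervention indicated". A trigger of more than a week sits awkwardly with both.

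**4. Does any text say which section governs?** None is visible. The lead-in to Table 3 sends readers to Section 5.6.1 for steroid use, but that section is Diet. Section 5.5.1.1 sends them to Section 5.2.1 for dose modification, but that section is Pretreatment Evaluations. Neither pointer ranks the two texts. The row headed General instructions at the top of Table 3 has no content in the copy reviewed, so a rule placed there cannot be excluded.

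**5. What follows on each reading?** If Table 3 gives the dose and 5.5.1.1 the timing, the longer wait for Grade 3 applies. If the two stand separately, they disagree on when to start. In either case the order of the waits inside 5.5.1.1 is unchanged.

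**The case against.** The best reply is that the two texts can be reconciled as steps. Table 3 gives an initial dose without a route. The Grade 3 or 4 line in 5.5.1.1 then adds intravenous and high-dose oral treatment if the event goes on for more than a week. The section does use escalation elsewhere, adding anti-inflammatory agents when steroids have not worked. On that reading Grade 3 has neither a wait nor a conflict. However, the colitis line does not say that it applies after steroids have failed. The reading is possible, but the text does not state it.

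Other parts of the reply stand and limit the point:

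- The measures are suggestions, and Sections 5.4.1 and 5.5.1 leave room to treat earlier. A reader might infer that the plan forbids steroids in the first week; nothing in it does.
- A reader might infer that the protocol has no rule of precedence. The unreadable General instructions row means this cannot be asserted.
- A reader might infer that Table 3 has no steroid direction for Grade 4. The higher-grade cells for pneumonitis, hypophysitis and nephritis are blank in the same way, which suggests cells merged across grades, so Grade 4 may already be covered.
- A reader might infer that the Grade 2 condition is equally wrong. The reversed order does not show that. Section 5.5.1.1 asks for other causes to be ruled out, and Table 3 itself refers to persistent Grade 2 events for other immune-related reactions, so a short persistence test can be a clinical choice.
- Urgent intervention and hospitalization in Table 6 do not in themselves mean steroids. Withholding or stopping Pembrolizumab, fluids, monitoring for perforation and GI consultation carry no wait.

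The need to exclude infection does not explain the order of the waits. Section 5.5.1.1 asks for other causes to be excluded for every disorder but sets a waiting period only for colitis, and sets the longer one for the graver grades. Investigator discretion permits earlier treatment but does not correct wording that supports delay.

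**Conclusion.** The point holds as a minor to moderate inconsistency in safety wording. Section 5.5.1.1 states a wait of more than 7 days for Grade 3 or 4 against more than 3 days for Grade 2, so the graver grades wait 4 days longer. Table 3 states no wait for Grade 2 or 3, and 9 of the 11 grade-specific steroid instructions in 5.5.1.1 have no persistence condition.

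The conclusion rests on reading the colitis lines as they stand, without an unstated escalation step, and on the steroid cell that is legible in the Grade 2 or 3 row of Table 3. It does not depend on the blank Grade 4 cell or on the absence of a precedence rule. The investigator's brochure, to which both sections refer, was not available, so the clinically intended wording cannot be settled here. The documents do not give the frequency of these events, so the number of patients affected is unknown. No endpoint, sample size or analysis in Section 8 changes.

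**What to change.** In Section 5.5.1.1, delete the one-week persistence condition from the Grade 3 or 4 diarrhea/colitis line. Events of those grades judged related to Pembrolizumab would then get intravenous followed by high-dose oral steroids with no waiting period. Keep the existing text on ruling out other causes, GI consultation and endoscopy.

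For Grade 2, ask the sponsor's clinicians to decide whether the 3-day condition applies, checking the current investigator's brochure, and make 5.5.1.1 and Table 3 say the same thing.

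The same amendment can correct two clerical cross-references: in 5.2.2.4.1 the pointer to 5.6.1 should be to 5.5.1, and in 5.5.1.1 the pointer to 5.2.1 should be to 5.2.2.4.1.

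The cost is a protocol wording amendment and a memo to sites, with no added procedures, visits or patients.

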### 5.5.1.2 Cisplatin

High dose Cisplatin is a highly emetogenic regimen with significant incidence of delayed nausea and vomiting. The following guidelines are suggested:

1. For acute nausea and vomiting, premedication should include a 5-HT3 antagonist, such as granisetron 1 mg iv; ondansetron, up to 16 mg iv; or palonosetron, 0.25 mg iv; plus a corticosteroid, such as dexamethasone, up to 20 mg iv. Fosaprepitant may also be included as premedication.
2. Breakthrough nausea and vomiting should be managed at the discretion of the medical oncologist or radiation oncologist.
3. Delayed nausea and vomiting (greater than 24 hours after chemotherapy administration) may be managed by the addition of aprepitant concurrently or with metoclopramide and dexamethasone.

